#### **FOR INDIVIDUAL PARTICIPANTS:**

Participants who develop a severe adverse event or laboratory abnormality will not receive any additional doses and will be monitored until resolution of the AE or the return of laboratory abnormality to the acceptable screening value(s). Study drug may be re-initiated after consultation with medical monitor and sponsor. Any participant with:

- elevated ALT or AST greater than 5 X ULN should have dosing with study drug stopped and have laboratory tests repeated every 3-4 days until levels return to less than or equal to 1.5 X ULN. If the medical monitor and investigator are in agreement, study drug may be continued while a confirmatory ALT/AST is obtained within 3 days. If the confirmatory ALT/AST tests are below 5 X ULN, study drug may be continued. The frequency of the laboratory tests may be modified after discussion with the medical monitor if the liver enzymes are in a decreasing trend.
- Elevated ALT or AST greater than 3 X ULN in combination with total bilirubin > 2 X ULN or INR > 1.5 X ULN OR an ALT or AST > 3 X ULN with the appearance of fatigue, nausea, vomiting, right upper quadrant pain or tenderness, fever, rash, and/or eosinophilia (>5%) should have dosing with study drug stopped and have laboratory testing repeated every 3-4 days. If the medical monitor and investigator are in agreement, study drug may be continued while a confirmatory laboratory testing is obtained within 3 days. If these criteria are no longer met, study drug can be continued at the discretion of the medical monitor and investigator. The frequency of the laboratory tests may be modified after discussion with the medical monitor if the laboratory tests are trending towards normal.
- An increase in serum creatinine by 0.3 mg/dL (24.4 micromol/L) or 150% of baseline that is without clinical explanation of another etiology will result in repeated serum chemistry testing within 3-7 days. If the serum creatinine elevation is confirmed on repeated testing the study drug will be discontinued. If the serum creatinine elevation resolves upon

subsequent testing after study drug is discontinued the study drug may be restarted with serum creatinine monitoring at the discretion of the medical monitor and investigator.

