#### **8.2 Duration of Study**

Each participant and caregiver will participate in a screening period of up to 60 days, followed by the primary double-blind treatment period of 24 weeks (169 days +/-2) followed by an optional double-blind extension treatment period of another 24 weeks (337 days +/-2). A follow up visit will occur 2 weeks after the last day of dosing. Including the screening period, the total duration of participant participation in the study is up to 36 week for the primary study or up to 60 weeks for the extension study. If a delay occurs with subjects progressing from the primary study to the extension study, a maximum of 4 weeks will be permitted.

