#### **9.5 *Participant Withdrawal Procedures***

##### **9.5.1 *Follow-up Procedures for Participants Who Withdraw Prematurely***

The date and the reason for study drug discontinuation or participant withdrawal from the study must be recorded on the Case Report Form. Participants who prematurely discontinue the study for any reason will be asked to attend the final/ early discontinuation visit but are not required to attend a follow up visit unless deemed necessary at the discretion of the investigator.

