Key for Schedule of Assessments

1. Informed consent must be obtained prior to the participant undergoing any study-specific procedures.
2. Confirm AD diagnosis (NIA-AA 2011 criteria, McKhann et al, 2011)].
3. Perform brain amyloid imaging (PET scan). Amyloid imaging of the brain may not be required if there is evidence of positive Alzheimer's disease biomarkers based on amyloid PET imaging or CSF A $\beta$ .
4. Cognitive testing will include the ADAS-Cog 14 and NTB. Cognitive assessments will be locally administered by trained site staff and then centrally scored by a qualified central reviewer. Sites will be provided with copies of the scored assessments for their own records.
5. Functional testing will include CDR-SB, ADCS-CGIC and ADCS-ADL
6. Vital signs will include body temperature, seated systolic and diastolic BP, pulse rate and respiratory rate (Section 15.1.5).
7. Coagulation panel may be repeated upon admission as medically indicated or required by local practice.
8. Serology for hepatitis B (HbsAg), hepatitis C (HCV) and HIV (Section 14.2).
9. Clinical laboratory testing (Section 14).
10. Height will be recorded only at screening; Weight will be collected at every visit. (Section 15.1.3).
11. During Screening (post-consent), only SAEs related to a study-specific procedure will be collected. For all related AEs of moderate or severe intensity ongoing at the end of the study, follow-up will continue until the event has resolved to baseline severity, the event is assessed as stable by the Investigator, or the patient is lost to follow-up or the patient withdraws consent.
12. CSF Sampling: (see Section 11).
13. Blood collection (see Section 14).
14. On clinic visit dates, subject should hold dose in AM and dosing should occur in the clinic.

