#### **10.2.12 Visit 11, Study Day 169 (For Primary Study only: End of Treatment / Early Discontinuation)**

For subjects participating in the Primary Study only **and not participating in the Extension Study**, this visit will serve as the end of treatment visit.

The following procedures will be conducted on Day 169: ( $\pm 7$  days):

- Perform MMSE
- Perform cognitive testing and functional assessments (see Section 16)
- Administer C-SSRS (see Section 16.1 for details)
- Perform physical examination (see Section 15.1.3 for details)
- Measure and record vital signs and weight (see Section 15.1.5 for details)
- Perform 12-lead ECG (see Section 15.1.6 for details)
- Draw blood and prepare sample for serum chemistry and hematology (see Section 14.1 for details) as well as for coagulation testing (prothrombin time [PT/INR]).
- Collect urine sample for urinalysis (see Section 14.1 for details)
- Draw blood and prepare samples for PK
- Perform  $^{11}\text{C}$ -UCB-J Imaging
- Perform  $^{18}\text{F}$ -FDG Imaging
- Perform MRI Imaging
- Perform a lumbar puncture and collect CSF samples for PK and PD analyses
- Record concomitant medications
- Record any SAEs that have occurred since the last visit
- Administer dose of study drug
- Perform study drug accountability

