**10.2.17 Extension Study - Visit 15, Study Day 337 / End of Treatment / Early Discontinuation**

The following procedures will be conducted on Day 337: ( $\pm 7$  days):

- Perform MMSE
- Perform cognitive testing and functional assessments (see Section 16)
- Administer C-SSRS (see Section 16.1 for details)
- Perform physical examination (see Section 15.1.3 for details)
- Measure and record vital signs and weight (see Section 15.1.5 for details)
- Perform 12-lead ECG (see Section 15.1.6 for details)
- Draw blood and prepare sample for serum chemistry and hematology (see Section 14.1 for details) as well as for coagulation testing (prothrombin time [PT/INR]).
- Collect urine sample for urinalysis (see Section 14.1 for details)
- Draw blood and prepare samples for PK
- Perform  $^{11}\text{C}$ -UCB-J Imaging
- Perform  $^{18}\text{F}$ -FDG Imaging
- Perform MRI Imaging

- Optional - Perform a lumbar puncture and collect CSF samples for PK and PD analyses
- Record concomitant medications
- Record any SAEs that have occurred since the last visit
- Administer final dose of study drug
- Perform study drug accountability

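### The shared end-of-treatment/early-discontinuation lists for Visits 11 and 15 include a study drug dose, which conflicts with the individual stopping rules, and the protocol is inconsistent on the follow-up visit for early discontinuers

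*Protocol*

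**What the plan says.** **Dosing at the visit.** Section 10.2.12 heads Visit 11 "For Primary Study only: End of Treatment / Early Discontinuation", and Section 10.2.17 is headed "Visit 15, Study Day 337 / End of Treatment / Early Discontinuation". The Visit 11 column of Table 1 and the Visit 15 column of Table 2 carry the same double label. Each section gives a single list. The Visit 11 list contains "Administer dose of study drug" and the Visit 15 list "Administer final dose of study drug".

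**Stopping rules.** Section 7.3.1, for individual participants, states: "Participants who develop a severe adverse event or laboratory abnormality will not receive any additional doses". It allows re-initiation after consultation with the medical monitor and sponsor. The synopsis repeats this. Section 9.4 counts the 7.3.1 events among the reasons for withdrawal, and Section 9.5.1 asks everyone who leaves the study prematurely, whatever the reason, to attend the early discontinuation visit.

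**Follow-up visit.** Section 8.2 says: "A follow up visit will occur 2 weeks after the last day of dosing". The synopsis paragraph on duration says the same in substance. Section 9.5.1, and the study procedures paragraph of the synopsis, say that early discontinuers "are not required to attend a follow up visit unless deemed necessary at the discretion of the investigator".

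**The concern.** A site that works from the visit list and a site that works from the stopping rules would act differently for the same participant. The participants concerned include those stopped for a confirmed liver enzyme, creatinine or calcium finding, and safety and tolerability is the primary objective. Section 4.2.1 names hypercalcemia and renal tubular damage as the dose-limiting toxicities in animals. These show up on laboratory tests more reliably than in what a participant reports, so it matters whether a laboratory visit after the last dose is required.

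The follow-up question also affects the safety tables. The SAP (Section 5.5) counts any event with onset at or after first dose as treatment-emergent, and Section 5.6 does not impute missing safety values. Completers therefore have one more scheduled occasion on which an abnormality can be found.

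**Working it through.** The plan states no figure on this point, so the check is to read the passages against each other and subtract visit days.

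1. **Who attends.** Section 9.4 makes a 7.3.1 event a reason for withdrawal, and Section 9.5.1 sends premature discontinuers to the combined visit. A participant withdrawn under 7.3.1 therefore meets the Visit 11 list (primary study) or the Visit 15 list (extension).
2. **What the list tells the site.** It gives a dosing line with no condition. The format does allow qualification: the Visit 15 lumbar puncture is marked optional. The dosing line carries no such mark.
3. **What 7.3.1 tells the site.** No further doses. Restart needs consultation with the medical monitor and sponsor or, for a creatinine or calcium rise that has resolved, is at the discretion of the medical monitor and investigator. The visit lists mention neither condition, so the restart clause does not remove the conflict.
4. **Whether other text settles it.** Footnote 14 of Tables 1 and 2 reads "On clinic visit dates, subject should hold dose in AM and dosing should occur in the clinic". It is attached to the row for dispensing study drug and concerns where and when a participant on drug takes the dose, so it adds little either way. The dosing lines elsewhere in Section 10.2 are not reliable enough to presume intent: Visit 13 (Day 253) lists a final dose although extension treatment runs to Day 337, and Visit 9 has no dosing line.
5. **Scope.** The direct conflict is limited to people stopped under 7.3.1. For someone who leaves for another reason, such as withdrawn consent, the dosing line is inconsistent with having discontinued but breaks no stopping rule.
6. **Required in-clinic observation after the last dose.**
   - Primary-only completers: 183 − 169 = 14 days; with the ±2 window, 12 to 16.
   - Extension completers: 351 − 337 = 14 days by Table 2, or 352 − 337 = 15 days by the heading of Section 10.2.18. Table and text differ by one day.
   - Early discontinuer dosed at the visit as listed: 0 days required after that dose.
   - Early discontinuer not dosed there: the visit is itself a post-drug safety assessment. Section 9.5.1 does not say how long after the last dose it should fall.
7. **What still applies to early discontinuers.** Section 7.3.1 requires monitoring of safety stoppers until the event or laboratory value resolves, with liver tests every 3–4 days for ALT/AST stops. Section 15.2.3 requires follow-up of any adverse event or clinically significant laboratory value, tracks unresolved events at least weekly (until resolution, for 30 days, or until loss to follow-up), and asks for self-report for 30 days. Section 15.3.2 collects SAEs to 30 days after last treatment. The early discontinuation visit includes examination, vital signs, ECG, chemistry, hematology, coagulation and urinalysis.

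Step 7 covers problems already known. What remains open is an abnormality not yet detected at the early discontinuation visit, and participants who leave for other reasons.

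**The case against.** The other side has three good arguments.

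**The lists were written for completers.** Section 10.2.12 introduces its procedures as those of Day 169, and the stopping rule is specific and categorical. A site would be unlikely to knowingly dose a stopped participant. This stands as a statement about likelihood. It does not remove the conflict, because the section headings and table columns apply the same list to early discontinuers.

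**The follow-up wording is a general rule with a stated exception.** The exception appears consistently in the synopsis and Section 9.5.1, and investigator discretion is a legitimate design choice. This largely stands. It supports a request to make the general statements and the exception refer to each other, not a finding that the exception is wrong.

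**Safety stoppers are monitored.** This stands, and it rules out two stronger inferences:

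- A reader might infer that post-drug safety data would be missing selectively in those who tolerated the drug worst. The documents do not support this. A participant stopped for a laboratory abnormality has been detected by a laboratory test and must be followed until it resolves.
- A reader might take the replacement allowance in Section 9.1 (25 − 21 = 4) as the number who could miss the follow-up visit. It is only a cap on replacements. Replacement is at the sponsor's discretion and applies to withdrawals that leave insufficient data, so it neither counts nor bounds early discontinuers.

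**Conclusion.** The dosing conflict is real on the text. For a participant withdrawn under 7.3.1, the Visit 11 and Visit 15 lists and the stopping rule give opposite instructions. The size is one listed dose per affected participant, assuming the list is followed literally. The documents give no basis for a count or proportion of participants.

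The follow-up point is weaker. Two statements of the rule are not reconciled, so a visit about 14 days after the last dose is scheduled for completers and discretionary for early discontinuers. The consequence is confined to the gap left after step 7 of the working. Together these are drafting faults that bear on safety and should be corrected. They are not evidence that the safety comparison is biased.

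**What to change.** 1. For Visits 11 and 15, set out the completer and early-discontinuation procedures separately in Sections 10.2.12 and 10.2.17 and in Tables 1 and 2. Reconcile the dosing lines with the stopping rules in the synopsis and Section 7.3.1, so that no site can read both instructions for one participant.
2. Reconcile the duration paragraph of the synopsis and Section 8.2 with the study procedures paragraph of the synopsis and Section 9.5.1, so that it is clear whether the follow-up visit applies to early discontinuers. The Day 351/352 difference can be corrected in the same edit.

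Which clinical rule prevails in each case is for the sponsor to decide. The cost is protocol wording. If the sponsor decides that the follow-up visit applies to early discontinuers, there would also be some extra attendances at a visit that already exists.

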**10.2.13 Primary Study - Visit 12, Day 183 (14 days +/-2)**

- Physical examination
- ECG
- Vital signs, weight
- Hematology, biochemistry
- Urinalysis

**10.2.14 Extension Study - Visit 12E, Day 211 (+/-3)**

- Perform physical examination (see Section 15.1.3 for details)
- Measure and record vital signs and weight (see Section 15.1.5 for details)
- Draw blood and prepare sample for serum chemistry and hematology
- Collect urine sample for urinalysis (see Section 14.1 for details)
- Record concomitant medications
- Record any SAEs that have occurred since the last visit
- Perform study drug accountability

**10.2.15 Extension Study - Visit 13, Day 253 (+/-3)**

- Perform MMSE
- Perform cognitive testing and functional assessments (see Section 16)
- Administer C-SSRS (see Section 16.1 for details)
- Perform physical examination (see Section 15.1.3 for details)
- Measure and record vital signs and weight (see Section 15.1.5 for details)
- Perform 12-lead ECG (see Section 15.1.6 for details)
- Draw blood and prepare sample for serum chemistry and hematology
- Collect urine sample for urinalysis (see Section 14.1 for details)
- Draw blood and prepare samples for PK
- Record concomitant medications
- Record any SAEs that have occurred since the last visit

- Administer final dose of study drug
- Perform study drug accountability

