**DURATION OF STUDY:**

Each participant and caregiver will participate in a screening period of up to -60 days, followed by the primary double-blind treatment period of 24 weeks (169 days +/-2), followed by an optional double-blind treatment period of an additional 24 weeks (337 days +/-2). A follow up visit will occur 2 weeks after completion of dosing. Including the Screening period of 60 days, the total duration of participant participation in the study is up to 36 weeks for those undergoing the first six months of treatment and the follow up visit only and up to 60 weeks for those undergoing both six month double blind treatment periods. If a delay occurs with subjects progressing from the primary study to the extension study, a maximum of 4 weeks will be permitted. It is anticipated that enrollment will occur over 15 months and all protocol activities will be completed after 21 months, with an additional 3 months for data analysis.

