**Table 2 - Schedule of Assessments –Primary and Extension Study**

Visit Name and Number	V1				Baseline V2	V3	Blood draw only	V4	V5	V6	V7	V8	V9	V10	V11	V12 E	V13	V14	Final / Early Discontinuation V15	V16
	Step 1	Step 2	Step 3	Step 4																
Study Day	-60 to -1				1	15 (+/-2)	21 (+/-1)	29 (+/-2)	43 (+/-2)	64 (+/-2)	85 (+/-7)	106 (+/-2)	127 (+/-2)	148 (+/-2)	169 (+/-7)	211 (+/-3)	253 (+/-3)	295 (+/-3)	337 (+/-7)	351 (14 D (+/-2) from V15)
Informed consent capability	x																			
Written informed consent 	x																			
Demographic information	x																			
General medical, surgical and psychiatric history	x																			
Inclusion/exclusion criteria	x	x		x																
Modified Hachinski	x																			
Geriatric Depression Score	x																			
C-SSRS	x					x														
Diagnosis of Probable AD 	x																			
 F-FDG Imaging																				
 C -UCB-J Imaging (SV2A imaging)																				
Amyloid imaging (e.g.  C -PiB Imaging) 																				
MR Imaging (Safety MRI, resting state BOLD)		x																		
MMSE	x																			
ADAS-Cog 14, NTB 																				

Visit Name and Number	V1				Baseline V2	V3	Blood draw only	V4	V5	V6	V7	V8	V9	V10	V11	V12 E	V13	V14	Final / Early Discontinuation V15	V16
	Step 1	Step 2	Step 3	Step 4																
Study Day	-60 to -1				1	15 (+/-2)	21 (+/-1)	29 (+/-2)	43 (+/-2)	64 (+/-2)	85 (+/-7)	106 (+/-2)	127 (+/-2)	148 (+/-2)	169 (+/-7)	211 (+/-3)	253 (+/-3)	295 (+/-3)	337 (+/-7)	351 (14 D (+/-2) from V15)
CDR-SB 					X			X			X		X		X		X		X	
ADCS-CGIC 					X			X			X		X		X		X		X	
ADCS-ADL 					X			X			X		X		X		X		X	
Physical Examination	X				X	X	X	X	X	X	X	X	X	X	X	X	X	X	X	X
ECG	X				X		X				X				X				X	
Vital signs, weight  , 10	X				X	X	X	X	X	X	X	X	X	X	X	X	X	X	X	X
Hematology, biochemistry	X				X	X	X	X	X	X	X	X	X	X	X	X	X	X	X	X
Urinalysis	X				X	X	X	X	X	X	X	X	X	X	X	X	X	X	X	X
Coagulation 	X													X						
Serology: Syphilis, HIV, HepB, HepC 	X														X					
Thyroid panel (T3, T4, TSH), B12, folate 	X																			
APOE status	X																			
CSF sampling for PK and PD 															X					X
Plasma sampling for PK 					X	X	X	X	X	X	X	X	X	X			X	X	X	X
Dispense study drug 					X						X				X		X			

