**10.2.16 Extension Study - Visit 14, Day 295 (+/-3) -**

- Perform physical examination (see Section 15.1.3 for details)
- Measure and record vital signs and weight (see Section 15.1.5 for details)
- Draw blood and prepare sample for serum chemistry and hematology
- Collect urine sample for urinalysis (see Section 14.1 for details)
- Record concomitant medications
- Record any SAEs that have occurred since the last visit
- Perform study drug accountability

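### Visit 13 (Day 253) and Visit 15 (Day 337) both instruct the site to give the final dose; if the Visit 13 line is followed, the Month 12 data are collected about 12 weeks off drug

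*Protocol*

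**What the plan says.** Protocol Section 10.2.15, the procedure list for extension Visit 13 at Day 253 (±3 days), tells the site to "Administer final dose of study drug". Its heading does not mark the visit as end of treatment or early discontinuation.

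The same line appears in the list headed "10.2.17 Extension Study - Visit 15, Study Day 337 / End of Treatment / Early Discontinuation".

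Other parts of the protocol bear on when dosing ends:

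- **Section 8.2** describes the primary treatment period as "followed by an optional double-blind extension treatment period of another 24 weeks (337 days +/-2"). The Synopsis, Protocol Section 6.3 and SAP Section 4.3 give the same extension.
- **Section 8.2** also says "A follow up visit will occur 2 weeks after the last day of dosing". Table 2 places that visit (Visit 16) at Day 351, 14 days after Visit 15.
- **Section 10.2.16**, Visit 14 at Day 295, includes "Perform study drug accountability" but no dosing line.
- **Table 2** has a row "Dispense study drug" with marks that read as Visits 2, 7, 11 and 13. The Section 10.2.15 list has no dispensing line.

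On the analysis side, Protocol Section 17.4 limits the primary analysis to Month 6 and allows a second model run through Month 12. The SAP is firmer: Sections 9.3 and 10 say that separate 12-month analyses will be done, and Section 11.7 plans the same for the CSF markers.

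**The concern.** The line is a dosing instruction in a visit-by-visit procedure list, which is the part of the protocol a coordinator works from. The word *final* is also not routine there. Most earlier visits ask for that day's dose, and Visit 11, which ends treatment for participants who do not enter the extension, simply asks for a dose. Only Visits 13 and 15 say final.

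The narrative lists do not correct the problem. Within the extension section, Visits 12E and 14 contain no dosing line and no visit list mentions dispensing. Someone reading only Section 10.2 would see a final dose at Day 253, nothing dispensed, and no further dose until another final dose at Day 337.

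If the Visit 13 line is followed, the second half of the extension is untreated. The Day 337 results would still be analysed as Month 12 data under the randomised arm. I found no SAP rule that flags or sets aside assessments made after dosing has stopped, and a participant handled this way would have followed a written instruction, so would not obviously be recorded as a deviation. The plan aims at 7 participants per arm, entry to the extension is optional, and the documents do not say how many will enter. One or two participants handled differently could therefore carry real weight in a by-arm comparison.

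Safety timing would move as well. Section 15.3.2 ends the investigator's SAE reporting duty 30 days after last treatment. Section 15.2.2 runs collection to the follow-up visit plus 30 days, which limits that effect without removing the ambiguity.

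**Working it through.** Study-day arithmetic is all that is needed; no power or error-rate formula applies.

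**Inputs**

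| Item | Value | Source |
|---|---|---|
| Visit 11, end of primary period | Day 169 | Protocol 10.2.12 |
| Visit 13 | Day 253, ±3 days | Protocol 10.2.15 |
| Visit 15 | Day 337, ±7 days (±2 in Section 8.2) | Protocol 10.2.17, 8.2 |
| Visit 16, follow-up | Day 351 (heading of 10.2.18: Day 352) | Table 2, 10.2.18 |
| Plasma half-life | about 12 hours | Protocol 4.3, healthy volunteers |

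**1. The plan's own figure.** Extension length = (337 − 169)/7 = 168/7 = 24.0 weeks. This reproduces the stated 24 weeks.

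**2. Final dose read as Day 337.** Extension dosing lasts 168 days. Follow-up at Day 351 is 351 − 337 = 14 days after the last dose, which agrees with the 2 weeks in Section 8.2.

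**3. Final dose read as Day 253.**

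- Extension dosing = 253 − 169 = 84 days = 12 weeks, and 84/168 = 50% of the stated period.
- Interval from last dose to the Day 337 assessments = 337 − 253 = 84 days = 12 weeks.
- With the visit-list windows, the shortest interval is (337 − 7) − (253 + 3) = 330 − 256 = 74 days and the longest is (337 + 7) − (253 − 3) = 344 − 250 = 94 days. With the ±2 days of Section 8.2 the range is 335 − 256 = 79 to 339 − 250 = 89 days.
- In half-lives: 84 × 24/12 = 168, with 148 and 188 at 74 and 94 days. Plasma drug would be gone at Day 337 by any reasonable margin.
- Follow-up at Day 351 would be 351 − 253 = 98 days after the last dose instead of 14. Two weeks after Day 253 is Day 267, when no visit is scheduled.
- Thirty days after Day 253 is Day 283, which precedes Visit 14 (Day 295) and Visit 15.

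**4. Which assessments are exposed.** Section 10.2.17 lists UCB-J PET, FDG PET, MRI, MMSE, cognitive and functional tests, PK blood and an optional lumbar puncture at Visit 15. These feed the 12-month analyses in SAP Sections 9.3, 10 and 11.7 and the Visit 15 concentrations in SAP Section 11.1. SAP Section 11.2 sets plasma values below quantification to zero, so off-drug samples would enter the concentration summaries as zeros.

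**5. Consistency with the rest of the text.** The 24-week extension, the Visit 15 heading, drug accountability at Visit 14, the follow-up interval and the Table 2 dispensing mark at Visit 13 all presuppose dosing after Day 253. I found no other text that supports ending it there. The Table 2 reading depends on column position in text where several rows have lost marks, so it should be checked against the formatted table. Its marks at Visits 2 and 7 do agree with Sections 10.2.2 and 10.2.8, and the contradiction stands without it.

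**The case against.** The strongest reply is that this is a drafting slip, not a flaw in the design. The extension is described consistently in the Synopsis, Protocol Sections 6.3 and 8.2 and SAP Section 4.3, and one bullet disagrees. Its wording is identical to the Visit 15 bullet, so a carried-over line is a plausible explanation, although that is inference. To act on it, a site would have to overlook the Visit 15 heading and its own final-dose line, the continuing drug accountability and the stated length of the extension. The 84 days is the gap between two visits and says nothing about how many participants, if any, would be affected.

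The reach is also limited. The primary objective is safety and tolerability. The primary efficacy and imaging analyses end at Month 6, before Visit 13. The extension and the Visit 15 lumbar puncture are optional, and Protocol Section 17.4 only permits the 12-month model.

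Most of this stands, and it bounds the harm: the error is unlikely rather than expected, and only Month 12 results are exposed. It does not remove the contradiction. The two lines cannot both apply to the same participant, the subject is dosing, and the SAP commits to the 12-month analyses that the protocol leaves optional.

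**Conclusion.** The concern holds. The protocol gives a final-dose instruction at two visits 84 days apart, and the Visit 13 line conflicts with the stated 24-week extension. If it were followed, the participant would receive 84 of 168 days of extension treatment, and the Month 12 assessments would be made 74 to 94 days after the last dose.

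The size is conditional. It applies only to extension participants handled under the Visit 13 line, and the documents give no basis for estimating their number. The direction and size of any effect on the Month 12 estimates cannot be derived either, because they depend on how quickly a treatment effect would fade. The off-drug conclusion assumes that the half-life of about 12 hours seen in healthy volunteers is roughly right in this population; with 84 days elapsed, the conclusion is insensitive to that figure. The Month 6 primary analyses are not affected.

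This is an internal inconsistency that should be corrected, because the correction is cheap and the instruction is operative.

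**What to change.** The sponsor should reconcile Protocol Sections 10.2.15, 10.2.17 and 8.2 and Table 2 so that exactly one extension visit is labelled as the final dose. Which visit that is, and how dosing runs between visits, is for the sponsor and investigator to confirm. The same edit should make the dispensing marks in Table 2 and the extension visit lists agree.

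The cost is about one line in an amendment or clarification letter. Because the line concerns dosing, the sponsor needs to decide whether it counts as administrative or substantial under Section 18.1.1.

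Two checks should accompany the edit. For any extension participant already past Visit 13, confirm the actual last-dose date from the dispensing and accountability records before Day 337 results are described as 12 months of treatment. In the SAP, add a sentence saying how assessments made after dosing has stopped will be identified in the 12-month efficacy, imaging, CSF and concentration summaries. Neither check needs new data collection.
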